11.2.1 Handling of values below a threshold

For the calculation of qRT-PCR parameters, any value which is not recorded as a number but expressed as a value below a detection limit will be imputed by half the value of the declared detection limit itself. For samples reported as qRT-PCR negative the value will be imputed to zero.

qRT-PCR examples:

- If the database contains values like “<2.18”, half the value of the detection limit (1.09) will be used for calculating parameters.
- If the database contains values like “NEG”, zero will be used for calculating parameters.

For the calculation of TCID₅₀ parameters, any value which is not recorded as a number but expressed as a value below a detection limit will be imputed to half the value of the declared detection limit for the first sample and the remainder values expressed as a value below a detection limit will be imputed to zero. qPCR negative samples that are not tested for TCD50 will be imputed to zero.

TCID₅₀ example:

- If the database contains values like “<0.75”, the following rules will be used for calculating parameters
 - 0.375 will be used for the first value reported as “<0.75”,
 - zero will be used for all remaining values reported as “<0.75”

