A total of 46 subjects were treated with VIS410 (n=33) or placebo (n=13) across 5 cohorts. Cohorts were performed sequentially and included different pretreatment regimens used to mitigate the GI events observed with VIS410. Preliminary findings from the first 31 subjects are presented below.

Preliminary Efficacy Data

A partially blinded pre-specified interim analysis of the first 3 cohorts was conducted to evaluate the safety and efficacy of the 2300 mg VIS410 dose and to determine whether dose escalation was appropriate. The distribution of subjects is presented in Table 3.

Table 3. Distribution of Subjects

Treatment	No. Dosed	Per Protocol*	No. Infected**
Placebo	13	9	7
VIS410 (2300 mg)	18	16	13
Total	31	25	20

HAI = hemagglutinin inhibition assay positive seroconversion at Day 14 or 28.

*Subjects with HAI >10 at baseline excluded per inclusion/exclusion criteria.

**Infected subjects who are either polymerase chain reaction positive or HAI positive.

Based on the preliminary results, VIS410 2300 mg dose demonstrated a statistically significant antiviral effect with a 76% and 91% reduction in nasopharyngeal viral AUC by

quantitative reverse transcriptase polymerase chain reaction (qRT-PCR) and half-maximal tissue culture infective dose (TCID₅₀) compared to placebo (Table 4).

Table 4. Viral Load and AUC Data

Viral Measure	Placebo (N=7)	VIS410 (N=13)	Reduction (%)	p Value*
Median Viral AUC TCID ₅₀ (log ₁₀ X hours)	546	45	92	0.019
Median Viral AUC qPCR (log ₁₀ X hours)	1031	235	77	0.024
Median Peak Viral Load TCID ₅₀ (log ₁₀)	5.0	2.7	2.2	0.009
Median Peak Viral Load qPCR (log ₁₀)	7.1	5.6	1.5	0.043

*Calculated with Mann-Whitney U Test.

In addition, analysis of the symptoms data demonstrated a trend in respiratory symptom resolution that was consistent with the virology data. Although this study was not powered to detect a statistical difference in symptom relief, a 2-day reduction in resolution of upper respiratory symptoms and AUC was observed in the VIS410 2300 mg group vs. placebo.

Preliminary Safety Data

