11.2 Nasopharyngeal Viral Load

Standard non-compartmental approaches using Phoenix WinNonlin (Pharsight Corporation, Princeton, NJ, USA; Version 7.0 or higher) will be used to calculate peak viral load (VL) and the area under the viral load-time curve (VL AUC). Viral load at each study visit, proportion of subjects with negative results at each study visit, peak VL, and VL AUC based on qRT-PCR and TCID₅₀ from nasopharyngeal secretions will be summarized with n, mean, SD, geometric mean, CV, minimum and maximum values in the mITT population overall and per influenza A virus subtype. All available viral data within the mITT population will be assessed to calculate proportion of subjects with negative results at each study visit. For all other calculated parameters, viral load will be assessed on all samples in the mITT population collected through the Day 7 visit. In addition, VL and VL AUC for the first 50 subjects will be listed through Day 14 (no summary statistics will be presented). For missing data on Day 3, Day 5 and Day 7, the analysis will be conducted without imputation and with the last observable measurement carried forward (LOCF). For missing data on Day 1, the analysis will be conducted by replacing the missing data with the Day 3 observable measurement. Subjects missing both Day 1 and Day 3 virology data will be removed from the analysis.

A t-test will be used to assess the difference between treatment groups in the VL AUC and peak VL from nasopharyngeal swabs based on qRT-PCR and TCID₅₀. If the assumptions needed for the t-test are not met, log transformation and/or non-parametric methods will be used.

Chi-square methods will be used to compare differences in treatment groups relative to placebo for the proportion of subjects with negative results on Day 3, Day 5 and Day 7 study visits.

A sensitivity analysis will also be performed; the data summary will be repeated in the mITT population excluding subjects who received antiviral therapy during the study. Determination of applicable antiviral therapy will be defined before the study is unblinded. All viral load data generated per the analytical plan will be listed.

For the influenza A virus subtype H3, virus load data measured by TCID₅₀ will be read out by both hemagglutination and NP-ELISA. The sensitivity is higher for NP-ELISA; therefore, all viral load parameters will be calculated using the data from NP-ELISA only.

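### If qRT-PCR load is recorded in log10, SAP 11.2.1 codes below-limit results well under half the detection limit, which can widen viral-load AUC differences between arms

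*SAP*

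**What the plan says.** SAP 11.2.1 sets two qRT-PCR rules. A result reported as below a limit "will be imputed by half the value of the declared detection limit itself"; the worked example begins "If the database contains values like “<2.18" and ends "half the value of the detection limit (1.09) will be used for calculating parameters". A negative result is handled separately: "For samples reported as qRT-PCR negative the value will be imputed to zero". The rules are the same in every arm, and neither 11.2 nor 11.2.1 gives a unit or scale.

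The coded values enter the visit summaries, peak load and viral-load AUC in SAP 11.2. The last two are compared between groups: "A t-test will be used to assess the difference between treatment groups in the VL AUC and peak VL from nasopharyngeal swabs". Log transformation or non-parametric methods are the fallback. Both measures are secondary endpoints (Protocol 3.2, SAP 3.2).

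The only direct clue to the scale is Protocol 1.3, Table 4, for the earlier challenge study. Its row "Median Peak Viral Load qPCR (log" carries a base-10 unit, and its row "Median Viral AUC qPCR" is in log10 x hours.

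**The concern.** Half a detection limit is a common substitute for a value known only to lie below that limit. It is half on the scale of measurement. If the database holds log10 values, dividing the recorded number by two takes the square root of the limit, which is a much smaller quantity. Coding negatives as 0 on that scale places them at one unit, lower still.

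Applying the rule equally to all arms does not make it neutral. An arm that clears virus sooner, or whose cleared samples are more often reported as NEG than as <2.18, receives more of the very low codes. Part of the reported AUC difference then depends on a coding distance for which the SAP gives no reason. The planned sensitivity analysis excludes subjects who took antivirals, and the LOCF repeat concerns missing visits. Neither varies the below-limit codes.

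**Working it through.** **Inputs.** From SAP 11.2.1: limit 2.18, code 1.09 for <2.18, code 0 for NEG. From the visit schedule: nominal Days 1, 3, 5 and 7, taken as 0, 48, 96 and 144 h. Assumption: 2.18 is log10, as in Protocol Table 4.

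**The plan's own figure.** 2.18 / 2 = 1.09, so the SAP's arithmetic is reproduced.

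**Back-transformation.**
- Limit: 10^2.18 = 151.4 units.
- Half the limit: 75.7 units, or 2.18 − log10(2) = 2.18 − 0.301 = 1.88 log10.
- Code 1.09: 10^1.09 = 12.3 units. 12.3 / 151.4 = 8.1% of the limit, and 1.88 − 1.09 = 0.79 log10 below half of it.
- Code 0: 10^0 = 1 unit, which is 1.88 log10 below half the limit and 1.09 log10 below the <2.18 code.

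If 2.18 were linear, half of it would be exactly 1.09 and the <2.18 rule would be correct.

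**Effect on one subject's AUC** (linear trapezoid, log10 x h; BLQ means reported as <2.18):

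| Profile at 0, 48, 96, 144 h | SAP codes | All below-limit at 1.88 |
|---|---|---|
| 6, 4, BLQ, BLQ | 414.5 | 471.3 |
| 6, 4, NEG, NEG | 336.0 | 471.3 |
| 6, BLQ, BLQ, BLQ | 274.8 | 369.5 |
| 6, NEG, NEG, NEG | 144.0 | 369.5 |

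First row under the SAP codes: 48 × (6 + 4)/2 + 48 × (4 + 1.09)/2 + 48 × 1.09 = 240 + 122.2 + 52.3 = 414.5. The first two profiles differ by 78.5 and the last two by 130.8, only because of which below-limit report was returned.

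**Effect on a group mean.** Suppose percent negative differs by 20 points at one visit.
- If the other arm's 20 points are quantifiable, the extra contrast against coding negatives at 1.88 is 0.20 × 1.88 = 0.38 log10 at that visit.
- If they are <2.18, it is 0.20 × 1.09 = 0.22 log10.
- Day 3 or Day 5 carries 48 of the 144 h, so 0.38 becomes 0.38 × 48/144 = 0.13 log10 averaged over the AUC. Day 7 carries 24 h: 0.38 × 24/144 = 0.06.

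**Illustrative simulation.** All inputs are assumed, not taken from the documents: 50 per arm, 4,000 runs, baseline 6 (SD 1.2) log10, decline 0.8 per day (SD 0.3), residual SD 0.5, and half of below-limit results NEG unless stated.

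| Scenario | SAP codes: mean AUC gap; rejection rate | All at 1.88: mean AUC gap; rejection rate |
|---|---|---|
| Identical arms | 0.3; 0.045 | 0.5; 0.050 |
| Same loads, NEG share 30% v 70% | 15.8; 0.068 | −0.1; 0.048 |
| Decline 0.80 v 0.95 per day | 53.4; 0.265 | 39.7; 0.228 |

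In the last row the gap is 53.4 / 39.7 = 1.35 times as large, about one third more.

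**Zeros.** SAP 11.2 asks for geometric means and allows a log transformation. The log of 0 is undefined, so both fail wherever a summarised value is 0. Visit loads are the likeliest place. This holds on either scale.

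**The case against.** A reader might infer that the codes produce treatment differences by themselves. The documents do not support that: the rule is common to all arms, and in the simulation identical arms reject at 0.045. Some difference in how often, or in which form, samples fall below the limit must exist first.

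A reader might also infer that the assay cannot tell the two kinds of low result apart, so that giving them different codes is wrong. SAP 11.2.1 shows that the laboratory reports two distinct results. Ranking NEG below <2.18 is defensible; only the distance of 1.09 log10 lacks support.

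Nor does a wider gap mean an exaggerated effect. In the last simulated scenario the gap with no limit at all would be 0.15 × 144² / (2 × 24) = 64.8 log10 x h, larger than under either coding. The point is dependence on an unexplained code, not proven bias in favour of the drug.

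The scale is inferred from another study's table, and planning geometric means and a log transformation leaves it less certain. The SAP's wording and its 1.09 example agree with each other, so 1.88 is a reading of what half the limit should mean.

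Reach is limited too. Proportion negative and time to resolution depend on status, not on the imputed number. Peak load is little affected when the peak is quantifiable. P-values are informational (SAP 4.1), there is no formal testing (SAP 2.3), and the protocol says in 1.1 that the sample size does not support a statistical determination of efficacy.

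All of this stands and limits the point. It leaves the AUC estimates exposed. The non-parametric fallback does not remove the dependence, because AUC ranks still depend on the codes.

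**Conclusion.** The point holds in a limited form. Assuming 2.18 is log10, the code for <2.18 is 0.79 log10 below half the limit and the code for NEG is 1.88 log10 below it. Relative to coding at 1.88, this enlarges viral-load AUC differences when arms differ in their below-limit results. For a 20-point difference in percent negative at one visit, the upper figure is 0.38 log10 at that visit, about 0.13 averaged over the AUC, or 0.06 at Day 7. On a linear scale the complaint about 1.09 disappears, but the missing scale and the trouble with zeros remain. This is worth correcting before unblinding. It does not touch the primary safety objective.

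**What to change.** 1. State the scale and unit of qRT-PCR viral load in SAP 11.2.1.
2. If it is log10, impute <2.18 as log10(limit/2) = 1.88.
3. Keep one fixed, prespecified value for negatives, not above the <2.18 code. Using the limit itself (2.18) would rank a negative above a <2.18 sample coded 1.88.
4. As a sensitivity analysis, repeat the viral-load AUC comparison with one common value, 1.88, for all below-limit and negative qRT-PCR results.
5. Say how geometric means and any log transformation treat zeros.

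The TCID50 rule in the same section could be reviewed at the same time. There the first <0.75 becomes 0.375, while "zero will be used for all remaining values reported as" <0.75, so identical reports get different numbers by order alone.

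The cost is a few lines of SAP text and one repeated AUC table. The viral-load reduction may look somewhat smaller.

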11.3 Time to Resolution of Viral Load

Median time to cessation of viral shedding, determined by qRT-PCR and TCID₅₀ results, and the 95% CI about the median, will be presented for each treatment group. This analysis will use Kaplan-Meier methods. Additional exploratory statistical analyses may be conducted as appropriate. Time to resolution of viral load will be assessed on all samples in the mITT population collected through the Day 7 visit. For missing data on Day 3, Day 5, and Day 7, the analysis will be conducted without imputation and with the last observable measurement carried forward (LOCF). For missing data on Day 1, the analysis will be conducted by replacing the missing data with the Day 3 observable measurement. Subjects missing both Day 1 and Day 3

virology data will be removed from the analysis. Resolution of viral load is considered to be one BLQ or lower measurement with no samples following that which are greater than the BLQ.

The following virology parameters will be derived:

- Time to resolution of viral shedding from end of infusion
 - Number of days from end of infusion until virus is no longer detectable (at or below the limit of detection) with no samples following that are greater than the BLQ through Day 7 visit
 - If virus is still above level of detection at the end of the study, the last day of viral collection through Day 7 visit will be used
- Time to resolution of viral shedding from onset of symptoms
 - Number of days from onset of symptoms until virus is no longer detectable (at or below the limit of detection) with no samples following that are greater than the BLQ through Day 7 visit
 - If virus is still above level of detection at the end of the study, the last day of viral collection through Day 7 visit will be used

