¹⁷ Subjects will be observed during infusion and at least 2 hours after completing the infusion of VIS410 to allow monitoring for possible hypersensitivity reactions. VIS410 will be administered over 2 hours. Infusion time can be extended at discretion of the Investigator up to 4 hours based on local infusion-related symptoms. If any serious systemic reactions occur, the infusion of VIS410 can be slowed or stopped at the discretion of the Investigator.

¹⁸ Within 1 hour prior to VIS410 administration.

¹⁹ Sample collected within 30 minutes after completing the infusion of VIS410/placebo.

²⁰ Nasopharyngeal swabs will be obtained from both nostrils (1 swab per nostril).

²¹ Will be done for the first 50 subjects enrolled only.

²² If a subject presents with or reports influenza-like illness, additional swabs (1 swab per nostril) should be taken (see Section 7.1.5).

LIST OF ABBREVIATIONS AND DEFINITIONS OF TERMS

Abbreviation	Definition
ADA	Anti-drug antibody
AE	Adverse event
AESI	Adverse event of special interest
AUC	Area under the curve
AUC _{0-∞}	Area under the concentration-time curve extrapolated to infinity
AUC _{0-last}	Area under the concentration-time curve from time 0 to the last measurable concentration
CD-1	Cluster of differentiation 1
CL	Clearance
C _{max}	Maximum serum concentration
CRO	Contract Research Organization
DBA	Dilute Brown Non-Agouti
DBP	Diastolic blood pressure
DMID	Division of Microbiology and Infectious Diseases
DSMB	Data Safety Monitoring Board
EC ₅₀	Half-maximal effective concentration
EDC	Electronic data capture system
GCP	Good Clinical Practice
GI	gastrointestinal
GLP	Good Laboratory Practice
HA	Hemagglutinin
HAI	Hemagglutination inhibition assay
HIV	Human immunodeficiency virus
ICF	Informed Consent Form
ICH	International Conference on Harmonization
IEC	Independent Ethics Committee
IgG1	Immunoglobulin G1
IRB	Institutional Review Board
ITT	Intent-to-treat
IV	Intravenous
LSLV	Last Subject Last Visit
MedDRA	Medical Dictionary for Regulatory Activities
mITT	Modified intent-to-treat
NOAEL	No-observed-adverse-effect level
NSAID	Non-steroidal anti-inflammatory drug
PK	Pharmacokinetic
PO	Oral (by mouth)
qRT-PCR	Quantitative reverse transcriptase polymerase chain reaction
SAE	Serious adverse event
SAP	Statistical analysis plan
SBP	Systolic blood pressure
SUSAR	Suspected unexpected serious adverse reaction
t _{1/2}	Elimination half-life
TCID ₅₀	Half-maximal tissue culture infective dose

Abbreviation	Definition

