4.3 INCLUSION CRITERIA

Subjects meeting all of the following criteria are eligible to participate in this study:

- 1) Male and female subjects aged ≥18 years and <65 years
- 2) Women should fulfill one of the following criteria:
 - a) Post-menopausal; either amenorrhea ≥12 months or follicle stimulating hormone >40 mIU/mL as documented in their medical history.
 - b) Surgically sterile; hysterectomy, bilateral oophorectomy, or tubal ligation.
 - c) Women of childbearing potential participating in heterosexual sexual relations must be willing to use adequate contraception from screening until 60 days post-infusion, per Section 7.1.2.
- 3) Non-vasectomized (or vasectomized less than 6 months prior to dosing) male subjects who have a female partner of childbearing potential must use an effective birth control method (see Section 7.1.2) when having heterosexual intercourse, from screening until 60 days post-infusion.
- 4) Test positive for influenza A by Rapid Antigen Test performed with a commercially available test on an adequate nasopharyngeal specimen in accordance with the manufacturer's instructions

- 5) Presence of at least one respiratory symptom (cough, sore throat, or nasal symptoms) of moderate to severe intensity, or presence of at least one constitutional symptom (myalgia [aches and pains], headache, feverishness, or fatigue) of moderate to severe intensity
- 6) Onset of symptoms (time when the temperature was first measured as elevated [temperature of $\geq 100.4^{\circ}\text{F}$ or $\geq 38^{\circ}\text{C}$], OR the time when the subject experienced at least one respiratory symptom or at least one constitutional symptom) no more than 72 hours before the start of infusion
- 7) Subject is able and willing to comply with study procedures, as per protocol
- 8) Subject is able and willing to give voluntary written informed consent

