5.1.2 Modified Intent-to-Treat Population

The mITT population will include all subjects who receive IV study drug and are confirmed influenza A positive by a molecular test at the central virological laboratory.

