6 DEMOGRAPHICS AND BASELINE CHARACTERISTICS

6.1 Demographics and Baseline characteristics

Descriptive statistics of the general demographic and Baseline characteristics for each treatment group and overall will be presented. Baseline variables age (years), height (cm), weight (kg), body mass index (BMI, kg/m²), both baseline HAI titers (H1 and H3), and time since onset of influenza symptoms will be summarized with n, mean, SD, median, minimum and maximum; time to onset of influenza will also be dichotomized (< 48 hours or ≥ 48 hours) and summarized with counts and percentages. Counts and percentages will be presented for each category of gender, race, ethnicity, vaccination status, confirmed influenza A by method of diagnosis (RAT, PCR, TCID₅₀), and influenza subtype.

The demographic and Baseline data will be summarized in the ITT and mITT populations. All demography and Baseline data will be listed.

The following definitions and conversions will be used:

- Height (in) *2.54 = height (cm)
- Weight (lb) /2.2 = weight (kg)
- BMI = weight (kg)/ height² (m²)
- Time since onset of influenza (hours) = date/time of infusion start – date/time of onset of symptoms. If onset time is missing, it will be imputed as 00:00 on the 24-hour clock.

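### TCID50 time to resolution treats subjects who are culture-negative before dosing, and stay negative, as having cleared virus before treatment

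*SAP*

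**What the plan says.** SAP 11.3 defines the event: "Resolution of viral load is considered to be one BLQ or lower measurement with no samples following that which are greater than the BLQ". It sets the scope as follows: "Time to resolution of viral load will be assessed on all samples in the mITT population collected through the Day 7 visit". One derived variable is "Number of days from end of infusion until virus is no longer detectable"; a second starts at symptom onset. Kaplan-Meier medians with 95% CIs are reported by group, and no between-group test is named. A missing Day 1 value is replaced by the Day 3 value.

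The Day 1 swab is a pre-dose sample (Protocol Table 1, footnote 18): "Within 1 hour prior to VIS410 administration". The infusion lasts 2 hours and may be extended to 4 (Table 1, footnote 17).

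SAP 5.1.2 admits dosed subjects who are "confirmed influenza A positive by a molecular test at the central virological laboratory". Entry under Protocol 4.3 requires only that subjects "Test positive for influenza A by Rapid Antigen Test". SAP 6.1 tabulates "confirmed influenza A by method of diagnosis" separately for rapid antigen test, PCR and TCID50, so the plan allows for the methods to disagree.

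SAP 11.2 adds chi-square comparisons with placebo of the proportion negative on Days 3, 5 and 7, using all available mITT data.

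**The concern.** The definition asks for no earlier positive culture and no post-dose sample. A subject with no culturable virus before dosing and none later meets it on the pre-dose swab, so the event precedes treatment and cannot be credited to either arm. The same subject counts as negative on Days 3, 5 and 7.

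The SAP handles the same situation elsewhere. In 9.1.1, a subject without symptoms at baseline gets a FluPRO duration of zero. In 9.1.2, time to normal temperature is limited to subjects febrile at baseline. The virology sections have neither rule.

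The Day 3-for-Day 1 replacement makes this worse. A subject whose Day 1 swab is missing and who is negative on Day 3 and afterwards is treated as negative on Day 1, although the clearance may have followed dosing.

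Time to resolution of viral load is a named secondary endpoint, and the comparison with placebo is its purpose.

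**Working it through.** The documents give no effect size, power figure or baseline culture-negative share for these endpoints, so there is no stated figure to reproduce.

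**1. Timing of the pre-dose event.** Time from end of infusion = -(hours from swab to start + infusion hours).
- Shortest: -(0 + 2) = -2 hours, or -0.083 days.
- Longest: -(1 + 4) = -5 hours, or -0.208 days.
- In whole calendar days, with swab and infusion both on Day 1: 0.

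SAP 11.3 does not say which unit applies, sets no floor at zero, and gives no rule for negative times in Kaplan-Meier.

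**2. Effect on the median.** Let a share q of each arm be culture-negative before dosing and remain so, and let the others clear at a constant rate λ (assumptions). For t > 0 the proportion unresolved is (1 - q)·exp(-λt). Setting this to 0.5 gives a median of ln(2(1 - q))/λ, against ln 2/λ among culture-positives. The share of the true median difference kept is ln(2(1 - q))/ln 2:
- q = 10%: ln 1.8/ln 2 = 85%
- q = 20%: ln 1.6/ln 2 = 68%
- q = 30%: ln 1.4/ln 2 = 49%
- q = 40%: ln 1.2/ln 2 = 26%

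This treats time as continuous. With swabs only at Days 3, 5 and 7, the observed median would move in steps.

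**3. Effect on percent negative at Day 3.** Assumed: 40% (placebo) and 65% (VIS410) negative among baseline culture-positives; 45 placebo and 90 pooled VIS410 subjects; a share f culture-negative at baseline in both arms and still negative at Day 3.

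Observed proportion = f + (1 - f)·p, so the difference is 0.25·(1 - f). The z uses the pooled variance of a chi-square test: z = difference / √[p̄(1 - p̄)(1/45 + 1/90)]. Among culture-positives, p̄ = (45·0.40 + 90·0.65)/135 = 0.567, and the sample sizes shrink by (1 - f), so z = 2.76·√(1 - f).

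| f | Placebo | VIS410 | Difference (points) | z, all mITT | z, culture-positive only |
|---|---|---|---|---|---|
| 10% | 46.0% | 68.5% | 22.5 | 2.53 | 2.62 |
| 20% | 52.0% | 72.0% | 20.0 | 2.30 | 2.47 |
| 30% | 58.0% | 75.5% | 17.5 | 2.09 | 2.31 |
| 40% | 64.0% | 79.0% | 15.0 | 1.87 | 2.14 |

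**4. Does the smaller sample cancel the gain?** A simulation took 50 per arm, placebo median 4 days, rate ratio 2.0, swabs 2, 4 and 6 days after infusion, and 2,000 runs per setting (all assumed). The log-rank test was only a gauge, since SAP 11.3 names no test. Power for one dose against placebo was 0.59 under the literal rule and 0.75 in culture-positives at q = 20%, and 0.38 against 0.63 at q = 40%. The restricted analysis did better despite fewer subjects.

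**The case against.** Several points on the other side have force.

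- **Not every culture-negative subject is affected.** A reader might infer that anyone TCID50-negative before dosing is resolved at that swab. The definition also requires no later value above BLQ, and symptom onset may be recent, so some subjects may turn positive later. For the same reason it is not shown that these subjects cannot respond to treatment. This stands: the point is limited to those who stay negative.
- **Negative times are one reading.** A reader might infer that the rule necessarily yields impossible values. SAP 11.3 counts days and gives no clock formula, whereas SAP 6.1 writes out a date/time subtraction when it wants one. In whole days the result is 0. This also stands, but the event still precedes treatment.
- **The loss can be overstated.** An unpooled z gives 2.53 to 1.80 for all mITT against 2.67 to 2.18 for culture-positives. The planned chi-square supports the smaller gap tabulated above, and at 10% the loss is slight.
- **Low stakes.** The endpoint is secondary, SAP 4.1 makes p-values informational, and Protocol 1.1 says the sample size does not support statistically significant determination of efficacy. This limits the weight of the point but does not make the rule sound.
- **Partly visible already.** Baseline confirmation by TCID50 and percent negative by visit are to be tabulated, and qRT-PCR is analysed alongside. A reader could therefore see the baseline-negative counts, but the Kaplan-Meier analysis would not change.

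**Conclusion.** The gap is real, and no other section closes it. Under SAP 11.3, an mITT subject who is TCID50-negative before dosing and has no later value above BLQ is resolved before treatment, at 0 days or about -2 to -5 hours depending on the unit. The Day 1 replacement can add subjects whose clearance came after dosing.

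Dilution is the expected direction under randomization, not a certainty in one trial. With 50 per arm and a 20% share, the between-arm difference in that share has an SD of √(2·0.2·0.8/50) = 8 points, so chance imbalance can push a result either way.

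The size rests on the unknown baseline culture-negative share. Over the assumed 10% to 40%, a 25-point Day 3 difference becomes 22.5 to 15 points, and 85% to 26% of the median difference is kept. At the low end this matters little; at the high end it could hide a useful antiviral signal.

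A reader should not infer that the trial's main conclusion is at risk. The primary objective is safety, analysed in the safety population without reference to culture status.

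**What to change.** Amend SAP 11.2 and 11.3 before unblinding:

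- Make the main TCID50 time-to-resolution and percent-negative analyses those in mITT subjects with an observed pre-dose TCID50 above the limit.
- Do not fill Day 1 from Day 3 when defining this subset or timing resolution. Otherwise post-dose results would decide membership, and early clearers in the active arms could be dropped preferentially.
- Count resolution only from post-dose samples, and state whether time is in whole days or clock time.
- Report the number TCID50-negative and the number missing at pre-dose by arm.
- Keep the all-mITT version as secondary.

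Because membership depends only on a pre-dose measurement, the randomized comparison is preserved within the subset. The cost is a few sentences and repeated tables, with no new data. The downside is a smaller n, including the loss of subjects with no Day 1 swab.
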